Traction bronchiectases are uneven dilation of the bronchi and bronchioles as a result of the fibrotic shrinkage of the lung. Dilated bronchi may look like air strips with thin uneven (wavy) walls. Transversal dimension may show bronchi as cysts and bronchiole as microcysts in the peripheral parts of the lung. Location of the multiple air cysts around dilated bronchi may confound differentiation with the honeycombing symptom. Multidimensional reformations should be used for proper understanding of the morphological substrate.

Reticular abnormality

Reticular abnormality is a net of relatively thin lines, round- or polygon-shaped, on unchanged lung tissue or moderate lung opacity. Anatomically these lines represent abnormal interstitial lung elements resulting from intralobular interstitial tissue (less than 2 cm in size) thickening in UIP. These structures are usually presented with the fragments of acini septa. Septal lines (acini septa of a larger size), 1-2 cm in diameter, can also be involved in reticular abnormalities; however, they are usually less affected than smaller reticular elements.

Lung opacity (or ground-glass attenuation)

Lung opacity (or ground-glass attenuation) is a HRCT scialogical phenomenon characterized with mid-enhanced density of lung tissue, with lumina and walls of the bronchi, lung vessels, as well as foci and reticular abnormalities, if present. Morphological substrate of the lung opacity symptom is formed by the changes in the lung tissue with unaffected airness which are not captured by the CT acquisition. These changes may include thickening of the alveolar septa of any etiology, partial alveolar filling with different contents, alveolar shrinkage due to hypoventilation, enhanced lung perfusion and lung congestion. When honeycombing and traction bronchiectasis are not revealed, lung opacity may be one of the signs of active inflammation. When honeycombing and traction bronchiectasis are present, lung opacity is usually a sign of interstitial lung fibrosis.

Pirfenidone—F. Hoffmann-La Roche Ltd

Appendix 2

HRCT Protocol (cont.)

IPF exacerbations and complications

IPF exacerbation is characterized with appearance of new sites of lung opacity-like density and/ or sites of consolidation, or abrupt and fast exaggeration of the present alike abnormalities. Infiltration overlaps cortically on reticular abnormalities and honeycombing. In some cases honeycombing reduces partially or completely due to effusion in the cysts.

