Assessment of UIP signs

Assessment of UIP signs on HRCT will be performed using a semiquantitative method (see [Table 1-3](#)). Each lung will be divided vertically into three zones: upper zone, middle zone and lower zone. Margins between the zones on axial section are level of tracheal bifurcation and level of the right lower pulmonary vein. The upper lung zone is defined as the area of the lung above the level of the tracheal bifurcation, the lower lung zone is defined as the area of the lung below the level of the lower pulmonary vein and the middle lung zone is defined as the area of the lung between the upper and lower zones.

The HRCT findings will be graded on a scale of 1-4 based on the classification system: 1) normal attenuation; 2) reticular abnormality; 3) traction bronchiectasis; and 4) honeycombing. The presence of each of the above four HRCT findings should be assessed independently in three (upper, middle and lower) zones of each lung. The extent of each HRCT finding will be determined by visual estimation of the percentage (%) (to the nearest 5%) of parenchymal involvement in each zone, from 0 to 100. A total sum of all abnormalities in one zone of a lung cannot exceed 400%.

The score for each zone will be calculated by multiplying the percentage of the area by the mentioned above grading scale score (1-4). The zone scores for six zones of two lungs will be averaged to determine the total score for each patient. The overall HRCT score should be obtained by adding the averages for each index. The highest possible score is 400 points and the lowest score is 100 points using this calculation method.

The total score will be named as the “HRCT fibrosis score”. Semiquantitative assessment with HRCT fibrosis score calculation will be performed at initiation of treatment and 6 months later. For patients continuing therapy in real clinical practice after study completion additional assessment will be performed in a year of therapy.

Pirfenidone—F. Hoffmann-La Roche Ltd

Appendix 2

HRCT Protocol (cont.)

Table 1-3. Assessment of HRCT UIP signs in lungs.

Sign	Reticular abnormality	Honeycombing	Traction bronchiectases	Normal attenuation	Lung opacity
Upper zone RL ¹					
Middle zone RL					
Lower zone RL					
Upper zone LL ²					
Middle zone LL					
Lower zone LL					

¹ RL – right lung.

² LL – left lung.

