The sign ‘lung opacity’ will be qualified separately using methodology described above for other signs, and its change over time will be assessed outside the framework of a total summed index of fibrosis (HRCT fibrosis score). Lung opacity should be graded as reticular abnormality to calculate the score for each zone, i.e. the percentage (%) area of opacity in a zone should be multiplied by the score of 2.

References

Pirfenidone—F. Hoffmann-La Roche Ltd

164/Protocol ML39355, Version 2 dated 09-Jun-2018

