8.3. Exploratory Efficacy Analyses

eCRF form: “HRCT SCAN”, “ADVERSE EVENTS”.

HRCT fibrosis score

The HRCT findings will be evaluated using HRCT scoring system. One ILD radiologist will make assessments of 4 main findings in three zones of each lung. The six zone scores will be averaged to determine the total score for each patient. Score will be recorded at the initial diagnosis and after six and 12 months in a similar manner for further comparison. The mean \pm SD of HRCT fibrosis score like continuous variable will be determined obligatory at baseline, 6 months and optional at 12 months.

The values of HRCT fibrosis score at baseline, at Week 26 and Week 52 (optional) will be summarized in table with standard descriptive statistics for continuous variables and 95% CI for the mean.

Additionally, the absolute change of HRCT fibrosis score from baseline at Week 26 and Week 52 (optional) will be summarized in table with standard descriptive statistics for continuous variables and 95% CI for the mean.

The paired t-test will be performed to evaluate the changes in the variable from the baseline to Week 26 and Week 52 (optional), respectively. The type I error rate will be set to 5%.

Lung opacity (ground-glass attenuation)

The sign ‘lung opacity’ will be qualified separately using methodology described above for other signs, and its change over time will be assessed outside the framework of a total summed index of fibrosis (HRCT fibrosis score). Lung opacity should be graded as reticular abnormality to calculate the score for each zone, i.e. the percentage (%) area of opacity in a zone should be multiplied by the score of 2.

The lung opacity score at Baseline, at Week 26 and Week 52 (optional) will be summarized using standard descriptive statistics for continuous variables and 95% CI for the mean.

Additionally, the absolute change of lung opacity score from Baseline at Week 26 and Week 52 (optional) will be summarized in table with standard descriptive statistics for continuous variables and 95% CI for the mean.

**ML39355_STATISTICAL ANALYSIS PLAN_Final 2.0_17 June 2020**Exacerbations

An exacerbation will be defined as an AE with special criteria “Is this an exacerbation of IPF?” = “Yes”, i.e. only in case the exacerbation has led to death of a patient. Rate of exacerbation will be reported in three following tables:

- Exacerbation cases during treatment period (until Week 26).

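### As written, the HRCT fibrosis score gives normal lung 1 point per percent and opaque lung none, so opacity arising in normal lung lowers the score and breaks its stated minimum of 100

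*Protocol*

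**What the plan says.** Protocol Appendix 2 (Assessment of UIP signs) grades four findings from 1 to 4: "1) normal attenuation; 2) reticular abnormality; 3) traction bronchiectasis; and 4) honeycombing". One central reader estimates by eye, in 5% steps, the share of each of six lung zones that shows each finding. Each share is multiplied by its grade, and the results are averaged over the zones and added. Two limits are stated: "The highest possible score is 400 points and the lowest score is 100 points using this calculation method", and "A total sum of all abnormalities in one zone of a lung cannot exceed 400" per cent.

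Lung opacity (ground-glass attenuation) is treated differently. Table 1-3 gives it a column apart from normal attenuation. It has its own score, area times 2, and "its change over time will be assessed outside the framework of a total summed index of fibrosis (HRCT fibrosis score" is the rule for its relation to the total. The same appendix describes opacity as lung of raised density. It names new opacity or consolidation as the imaging mark of an exacerbation, and says that opacity seen together with honeycombing and traction bronchiectasis is usually fibrotic.

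SAP 8.3 then tests the fibrosis score: "The paired t-test will be performed to evaluate the changes in the variable from the baseline to Week 26 and Week 52 (optional), respectively", with a 5% type I error rate. The opacity score, FVC, the 6-minute walk and EQ-5D are summarised descriptively, with no test.

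**The concern.** A higher score is meant to indicate more fibrosis. Because normal lung carries a positive weight and opacity carries none, the score depends on how much of the zone is opaque as well as on how much is fibrotic. Lung that turns from normal to opaque, without a graded fibrotic sign, leaves the grade-1 area and nothing replaces it. The score falls although the lung looks worse. When that opacity clears, the score rises.

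Three features of the plan make this matter. The study has one arm, so a shift in the score is not cancelled by a comparator. The paired test is the only hypothesis test in either document, and Table 2.15 is the only efficacy table shell with p-values. And SAP 8.3 counts an exacerbation only if it was fatal. A survivor whose new opacity is still present on the Week 26 scan is absent from the exacerbation tables, but can still contribute a lower fibrosis score.

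**Working it through.** **Inputs** (all from Appendix 2). Let N, R, T, H and G be the percentages of a zone read as normal attenuation, reticular abnormality, traction bronchiectasis, honeycombing and opacity. The weights are 1, 2, 3, 4 and, because opacity is outside the sum, 0.

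Zone score as written: S = N + 2R + 3T + 4H.

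**Step 1: reproduce the stated range.** If the four graded findings fill the zone (N + R + T + H = 100), the smallest score is 100 × 1 = 100 and the largest is 100 × 4 = 400. The plan's figure is reproduced. If all four could each cover the whole zone, the maximum would be 100 × (1 + 2 + 3 + 4) = 1000, so the stated range implies that they share out the zone.

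**Step 2: let opacity take area.** If the five columns of Table 1-3 fill the zone and G has weight 0, the range is 0 to 400. Normal lung with 20% opacity in every zone scores 80 + 0 = 80, below the stated minimum.

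**Step 3: direction.** Moving x% from N to G changes S by −x. Moving it back changes S by +x. If opacity lies over fibrosis that is still read as fibrosis, the change is 0. Under the written rule new opacity never raises the score.

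**Step 4: examples.** The baseline zone is N 60, R 20, T 10, H 10, so S = 60 + 40 + 30 + 40 = 170. The last column uses the definition proposed under the fix, where the grade-1 area is N plus any opaque lung without a fibrotic finding.

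| Follow-up zone | As written | With the fix |
|---|---|---|
| 20% of normal turns opaque | 40 + 40 + 30 + 40 = 150 (−20) | 60 + 40 + 30 + 40 = 170 (0) |
| 10% of normal turns reticular, 10% turns opaque | 40 + 60 + 30 + 40 = 170 (0) | 50 + 60 + 30 + 40 = 180 (+10) |

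The second row shows real progression read as no change.

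**Step 5: patient level.** The six zones are averaged. New opacity of 5% in one zone gives −5/6 = −0.83 points; 20% in all six zones gives −20.

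**Step 6: dependence on an unwritten convention.** For the first row, the written rule gives −20. Recording the opaque lung as grade 1 gives 0. Rescaling to the non-opaque area gives 150/0.80 = 187.5, or +17.5. The last two conventions keep the 100 to 400 range, but neither is stated.

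**The case against.** The strongest reply is that the authors cannot have meant this. The stated minimum of 100 makes sense if opacity is an overlay: noted separately, with the lung beneath still recorded as normal attenuation unless it shows fibrosis. Opacity could then not move the score. That may well be the intention, but it is written nowhere. Table 1-3 separates the two columns, and the appendix describes opacity as raised density, so a reader following the text would not enter it as normal. The conflict with the minimum is a reason to write the rule down.

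Other parts of the reply stand:

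- The loss of 1 point per percent applies only to opacity arising in previously normal lung. A reader might infer that every exacerbation will register as improvement. The documents do not support that: Appendix 2 says exacerbation infiltrates overlie reticular change and honeycombing, and where that fibrosis is still read the score does not move.
- A reader might add that, in an exacerbation, "In some cases honeycombing reduces partially or completely due to effusion in the cysts". That is a visibility problem in a graded finding. It does not come from the zero weight of opacity, and the fix below does not cure it.
- The endpoint is exploratory. The opacity score is tabulated next to the fibrosis score (Tables 2.15 and 2.16) and listed by patient (Listing 22), so opposite movements can be seen. That helps interpretation but does not correct the p-value.

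**Conclusion.** The point holds in a limited form. As written, opacity arising in previously normal lung lowers the zone score by 1 point per percent, its clearing raises it by the same amount, and opacity over fibrosis that is still read leaves it unchanged. The rule is incompatible with the stated minimum of 100, because opaque area that scores nothing brings the possible minimum down to 0. It can bias the direction of change in the endpoint that carries the plan's only test.

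This rests on three assumptions: the reader keeps opaque lung out of the normal column, as Table 1-3 implies; the opacity lies in lung without a graded fibrotic finding; and readings are not rescaled to the non-opaque area.

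Two stronger readings are not supported. One is that the test result will be driven by opacity. The documents give no standard deviation for the score and no expected change in opacity, so only the direction and the points per percent are established. The other is that patients could plausibly enter with scores far below 100, for example 60% normal and 40% opaque, which scores 60. Table 1-2 treats ground-glass extent greater than reticular extent as inconsistent with UIP, and Table 2 in Protocol 4.5.6.2 makes such a scan ineligible. A composition like that is more plausible in a single zone or on a later scan.

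**What to change.** In Appendix 2 and SAP 8.3, define the grade-1 area as all lung in the zone that shows none of reticular abnormality, traction bronchiectasis and honeycombing, whether it is normal or opaque. Keep lung opacity as its own separately reported score. With non-overlapping findings the zone score becomes 100 + R + 2T + 3H, which restores the 100 to 400 range and cannot be moved by exchange between normal and opaque lung.

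If scans have already been read and the component percentages are in the database, report the sum of the grade 2 to 4 terms, 2R + 3T + 4H, as a sensitivity analysis. State that it is on a different scale: normal to reticular counts +2 per percent instead of +1, and the minimum is 0. Check first that the components are available. The SAP names only the total fibrosis score and the opacity score (Section 7.3, Listing 22), so it cannot be assumed that no re-reading would be needed.

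The cost is one sentence in each document and a small programming change, with no extra scans or readers. The small downside is a possible departure from the grading system that Appendix 2 cites.

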Appendix 3 Histopathologic Criteria for UIP Pattern

UIP Pattern (All 4 Criteria)	Probable UIP Pattern	Possible UIP Pattern (All 3 Criteria)	Not UIP Pattern (Any of the 6 Criteria)

 • Evidence of marked fibrosis/ architectural distortion, ± honeycombing in a predominantly subpleural/ paraseptal distribution • Presence of patchy involvement of lung parenchyma by fibrosis • Presence of fibroblast foci • Absence of features against a diagnosis of UIP suggesting an alternate diagnosis (see fourth column) 	
 • Evidence of marked fibrosis/ architectural distortion, ± honeycombing • Absence of either patchy involvement or fibroblastic foci • Absence of features against a diagnosis of UIP suggesting an alternate diagnosis (see fourth column) 
or
 
 • Honeycomb changes only^c 	
 • Patchy or diffuse involvement of lung parenchyma by fibrosis, with or without interstitial inflammation • Absence of other criteria for UIP (see UIP Pattern column) • Absence of features against a diagnosis of UIP suggesting an alternate diagnosis (see fourth column) 	
 • Hyaline membranes^a • Organizing pneumonia^{a,b} • Granulomas^b • Marked interstitial inflammatory cell infiltrate away from honeycombing • Predominant airway centered changes • Other features suggestive of an alternate diagnosis

^a Can be associated with acute exacerbation of idiopathic pulmonary fibrosis.

^b An isolated or occasional granuloma and/ or a mild component of organizing pneumonia pattern may rarely be coexisting in lung biopsies with an otherwise UIP pattern.

^c This scenario usually represents end-stage fibrotic lung disease where honeycombed segments have been sampled but where a UIP pattern might be present in other areas. Such areas are usually represented by overt honeycombing on HRCT and can be avoided by pre-operative targeting of biopsy sites away from these areas using HRCT.

Pirfenidone—F. Hoffmann-La Roche Ltd

165/Protocol ML39355, Version 2 dated 09-Jun-2018

Appendix 5

EuroQol-5D Questionnaire (cont.)

Reference

Appendix 4 Borg Scale

This instrument is to be self-administered by the patient as part of the 6MWT procedure. The patient will be given a paper copy of this instrument with the following instructions given in writing at the time the instrument is administered:

“Please rate the current severity of your breathlessness by circling the most appropriate number on the following scale.”

0 Nothing at all

0.5 Very, very slight (just noticeable)

1 Very slight

2 Slight (light)

3 Moderate

4 Somewhat severe

5 Severe (heavy)

6

7 Very severe

8

9

10 Very, very severe (almost max)

Reference

Borg GA. Psychophysical bases of perceived exertion. *Med Sci Sports Exerc* 1982, 14,5:377–81.

Pirfenidone—F. Hoffmann-La Roche Ltd

167/Protocol ML39355, Version 2 dated 09-Jun-2018

Appendix 5

EuroQol-5D-5L Questionnaire

Under each heading, please tick the ONE box that best describes your health TODAY.

MOBILITY

- I have no problems in walking about
- I have slight problems in walking about
- I have moderate problems in walking about
- I have severe problems in walking about
- I am unable to walk about

SELF-CARE

- I have no problems washing or dressing myself
- I have slight problems washing or dressing myself
- I have moderate problems washing or dressing myself
- I have severe problems washing or dressing myself
- I am unable to wash or dress myself

USUAL ACTIVITIES (e.g. work, study, housework, family or leisure activities)

- I have no problems doing my usual activities
- I have slight problems doing my usual activities
- I have moderate problems doing my usual activities
- I have severe problems doing my usual activities
- I am unable to do my usual activities

PAIN / DISCOMFORT

- I have no pain or discomfort
- I have slight pain or discomfort
- I have moderate pain or discomfort

Pirfenidone—F. Hoffmann-La Roche Ltd

168/Protocol ML39355, Version 2 dated 09-Jun-2018

Appendix 5

EuroQoI-5D Questionnaire (cont.)

I have severe pain or discomfort

I have extreme pain or discomfort

ANXIETY / DEPRESSION

I am not anxious or depressed

I am slightly anxious or depressed

I am moderately anxious or depressed

I am severely anxious or depressed

I am extremely anxious or depressed

[figure not shown]
Appendix 5

EuroQol-5D Questionnaire (cont.)

- We would like to know how good or bad your health is TODAY.
- This scale is numbered from 0 to 100.
- 100 means the best health you can imagine.
0 means the worst health you can imagine.
- Mark an X on the scale to indicate how your health is TODAY.
- Now, please write the number you marked on the scale in the box below.

YOUR HEALTH TODAY =

The best health
you can imagine

The worst health
you can imagine

Appendix 6 GAP Risk Assessment

	Predictor	Points	
G	Gender		
	Female	0	
	Male	1	
A	Age, y		
	≤60	0	
	61–65	1	
	>65	2	
P	Physiology		
	FVC, % predicted		
	>75	0	
	50–75	1	
	<50	2	
	DLco, % predicted		
	>55	0	
	36–55	1	
≤35	2		
Cannot perform	3		
Total Possible Points		8	
Stage	I	II	III
Points	0–3	4–5	6–8
Mortality			
1-y	5.6	16.2	39.2
2-y	10.9	29.9	62.1
3-y	16.3	42.1	76.8

Figure Legend

The GAP index and staging system.

Points are assigned for each variable of the scoring system to obtain a total point score (range, 0–8). Patients should be scored in the “Cannot perform” category for DLco if their symptoms or lung function prohibited performance of the DLco maneuver. If DLco is unavailable because it was not ordered or not completed because of nonrespiratory limitations, then the model cannot be applied. The total point score is used to classify patients as stage I (0–3 points), stage II (4–5 points), or stage III (6–8 points). Model-

Pirfenidone—F. Hoffmann-La Roche Ltd

Appendix 6 GAP Risk Assessment (cont.)

predicted 1-, 2-, and 3-y mortality is shown by stage. GAP = gender, age, and 2 lung physiology variables (FVC and DLco).

The formulas for computing predicted DL_{CO} are as follows (Crapo and Morris 1971):

Predicted DL_{CO} for men $0.410 \times \text{height (cm)} - 0.210 \times \text{age (yr)} - 26.31$

Predicted DL_{CO} for women $0.282 \times \text{height (cm)} - 0.157 \times \text{age (yr)} - 10.89$

References

Appendix 7

IPF Care Program

IPF Care Program by F. Hoffmann-La Roche Ltd (Switzerland)

[figure not shown]
Guidance for telephone calls to the patients participating in the clinical trial of pirfenidone

Telephone calls are scheduled at Weeks 3, 5, 7, 13 and 24. Optional calls can be performed at Weeks 8 and 10, if necessary.

A total number of calls is 5 to 7. Schedule of telephone calls and topics for discussion are detailed in the Figure below.

Appendix 7

IPF Care Program (cont.)

Answers to the questions in accordance with FAQ – IPF Care Program

A full version of the IPF Care Program will be supplied by the Sponsor to the investigators or other designated staff.

Pirfenidone—F. Hoffmann-La Roche Ltd

ILD	Interstitial lung disease
IPF	Idiopathic Pulmonary Fibrosis
LDH	Lactic dehydrogenase
LOCF	Last observation carried forward
MDT	Multidisciplinary team
(n)MWT	N-minute walk test
NCS	Not clinically significant
PFT	Pulmonary function test
PRO	Patient-reported outcome
PT	Preferred term
QTC-F	QT interval corrected (using Fridericia's formula)
RBC	Red blood cells
SAE	Serious Adverse Event
SAP	Statistical analysis plan
SD	Standard deviation
SOC	System organ class
SOP	Standard operating procedure
SSD	Sum of squared deviations
SLB	Surgical lung biopsy
TEAE	Treatment emergent adverse events
TID	Three times per day
TS	Treated set
UIP	Usual interstitial pneumonia

ML39355_STATISTICAL ANALYSIS PLAN_Final 2.0_17 June 2020

VAS	Visual Analogue Scale
WBC	White blood cells
yr	Year

2. Introduction

This SAP is written according to ICH E9 Guideline [1] and Data MATRIX LLC SOP [2, 3] using the Protocol Final version 2.0 dated 01.02.2019 and CRF Final version 1.2 dated 08.07.2019.

The purpose of this document is to provide a more technical and detailed elaboration of the principal features of the analysis, described in the Protocol, and to include detailed procedures for executing the statistical analysis.

The SAP needs to be finalized and signed prior to database soft lock. Revisions to the approved SAP may be made prior to database soft lock. In case of deviation from the finalized SAP, explanation will be provided in the clinical study report (CSR).

3. Study Objectives and Endpoints

